### **10.4. *Determination of sample size***

The sample size is for exploratory statistical analysis purposes only. There are no formal confirmatory hypotheses to be tested. The text in this section describes what can be observed with the current sample size.

Sample size calculation was performed using PASS 12 and SAS 9.2 (SAS Institute Inc., Cary, NC, USA).

The potential immune interference due to immunological stress to lymph nodes is assumed to result in decreases to all of the 4 B test strains but to various extents. In a previous study (MenABCWY-011 [V102\_15]), the GMT ratios ranged from 74% (-0.13 on log10 scale) to 50% (-0.3 log10 scale) with a mean of 64% (-0.19 on log10 scale). Because of this consistent decrease in GMT ratios in the MenABCWY group in comparison to the MenB group across the 4 serogroups, the presence of the lymph-node effect will be tested globally on all the serogroups together. A multivariate analysis of V102\_15 data provided an estimate of  $\sigma = 0.435$  (on log10 scale) for the standard deviation (SD) of the averaged GMTs across the 4 serogroups of the MenABCWY arm. That variability is higher than what would be expected by dividing the variance of a single serogroup by 4 due to the correlations existing between serogroups.

Therefore, assuming a SD of  $\sigma = 0.435$  (in log form), group sample sizes of 100 in each study group will achieve a power of approximately 80% to reject the null hypothesis of equal means when the population mean difference is -0.130 (log GMT ratio 74%) with a SD of 0.435 for both groups and a significance level (alpha) of 10% using a 1-sided 2-sample equal-variance t-test. This calculation ignores the potential correlation that might exist between serogroups of the MenABCWY when pooled together.

The numerical results for the 2-sample t-test assuming equal variance (alternative hypothesis:  $\delta < 0$ ) is shown in [Table 14](#).

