#### Analysis of hSBA GMT

An analysis of covariance (ANCOVA) model will be used to analyze post-vaccination log-transformed titers of hSBA for both the primary and secondary objectives (i.e. the hSBA at 1 month after the last vaccination and the hSBA at 1 month after the first vaccination, respectively). The ANCOVA model will be fitted to each serogroup/strain individually, and in addition the serogroup B strains will be grouped together to perform a pooled analysis. The GMTs obtained through the ANCOVA model will be called “adjusted” and the “unadjusted” GMTs will be obtained through descriptive statistics. Unadjusted and adjusted GMTs and associated 2-sided 80% CIs will be computed for each study group and for each strain at each visit. The fixed-effect model will include the age strata, treatment, serogroup, and center as fixed effects. The pre-vaccination log-transformed titer with centering at zero will be included as a continuous covariate. An interaction between serogroup and pre-vaccination log-transformed titer centered at zero will be included in the model. For each study group, adjusted GMTs and their 80% CIs will be obtained by exponentiating (base 10) the least squares means and the lower and upper limits of the 80% CIs of the log-transformed titers (base 10).

The following contrasts will be computed to investigate possible effects on the immune response based on strains common to each treatment group:

- a. rMenBOMV+ACWY\_S versus rMenBOMV+ACWY\_D (test for immune interference, due to immunological stress to lymph node)
- b. MenABCWY versus rMenBOMV+ACWY\_S (test for other unknown immunological interference)
- c. rMenBOMV+ACWY\_S versus rMenBOMV
- d. rMenBOMV+ACWY\_S versus MenACWY
- e. rMenBOMV+ACWY\_D versus rMenBOMV
- f. rMenBOMV+ACWY\_D versus MenACWY
- g. MenABCWY versus rMenBOMV
- h. MenABCWY versus MenACWY

In addition, the distribution of antibody titers for each strain will be displayed using reverse cumulative distribution curves.

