## 8 Immunogenicity Analysis

One of the main objectives of the study is to estimate the extent of a potential immune interference, due to immunological stress to lymph nodes in the arm where the combination vaccine is administered in comparison to injections in 2 different arms of individual vaccines. The sample size defines the conditions under which the observed reduction in immune response will be attributed to a true lymph-node effect or is the consequence of natural variability. An acceptable probability of falsely detecting the lymph-node effect was set to 10% (1-sided test). The minimum probability of detecting the lymph node effect is set to 80%.

Immune response will be measured using serum bactericidal assay using human complement (hSBA) testing performed on serum samples and titer results will be

analyzed for the immunogenicity analysis. Titers below LOD will be handled as described in Section 4.3.

The primary and secondary analysis will be based on PPSx. If the difference between PPSx and FASx is greater than 10%, a second analysis based on FASx will be performed to complement the PPSx analysis i.e. an analysis can be performed for PPS3 and FAS3, and for PPS4 only.

Titer results will be listed for the All Enrolled Set and the listing will indicate subjects included in each of PPSx and FASx. The listing will also indicate subjects with hSBA titers  $\geq$  LLOQ and subjects who experienced a 4-fold increase in hSBA titers since baseline.

For the remainder of Section 8 the Analysis Visit names defined in Table 4 will be used.

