ANCOVA1 for the immunogenicity analysis will be fitted in SAS using PROC MIXED. ANCOVA2 will be fitted using PROC MIXED with a REPEATED statement to account for within subject correlation. The TYPE =UN option will be used to specify an unstructured covariance model. The unstructured model was used to estimate sample study and does not make any assumptions about the form of the covariance structure in the data. The models will be fitted as follows:

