### ANCOVA1

- The fixed-effect model will include age strata, study group, and center as fixed effects. The pre-vaccination (Baseline) log-transformed titer with centering at zero will be included as a continuous covariate.
- The model will be fitted to each serogroup/strain\* separately.

\* a categorical variable will be used to indicate if the dependent variable (response) is for serogroup A, C, W-135, Y or individual serogroup B test strain M14459, 96217, NZ98/254 or M07-0241084.

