### ANCOVA2

- The fixed-effect model will include age strata, study group, strain\*\* and center as fixed effects. The pre-vaccination (Baseline) log-transformed titer with centering at zero will be included as a continuous covariate. An interaction between strain\* and pre-vaccination log-transformed titer centered at zero will be included in the model.
- The model will be fitted to the serogroup B test strain data only.

\*\* a categorical variable will be used to indicate if the dependent variable (response) is for serogroup B test strain M14459, 96217, NZ98/254 or M07-0241084.

For each study group, adjusted GMTs, SEs and 80% CI for GMT will be obtained by taking the anti-logarithm of the least squares means, the SE and the lower and upper limits of the 80% CIs of the log-transformed titers. The pre-vaccination log-transformed titer will be zero centered as follows: *log-transformed titer for each subject at Baseline – mean(log-transformed titer for all subjects at Baseline)* i.e. centering will occur after the titer results have been log transformed.

The contrasts in Table 6 will be computed at AVISIT 4 based on PPS3 to investigate possible effects on the immune response based on strains common to each study group.

No adjustment will be made for multiple comparisons.

rMenBOMV+ACWY\_S will be declared statistically inferior if the 2-sided 80% CIs of the ratio of the GMT with rMenBOMV+ACWY\_D as control is lower than 1 at 1 month after last vaccination. The lymph-node effect would therefore be the most probable cause for the decrease observed.

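### ANCOVA1 (and ANCOVA2) pool one residual variance over all groups in the fit, including the group never given the antigen, so the 80% CIs may be modestly too narrow

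*SAP*

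**What the plan says.** Below, S and D stand for rMenBOMV+ACWY_S and rMenBOMV+ACWY_D.

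- **Model.** SAP 8.1.1 states "ANCOVA1 for the immunogenicity analysis will be fitted in SAS using PROC MIXED". Under ANCOVA1, "The fixed-effect model will include age strata, study group, and center as fixed effects", with centered baseline log titer as covariate, fitted to each serogroup or strain separately. No REPEATED / GROUP= option, robust standard error or other provision for unequal variances is given. The general model sentence in Protocol 10.8, "The fixed-effect model will include the age strata, treatment, serogroup, and center as fixed effects", is equally silent.
- **Pooled B.** ANCOVA2 uses an unstructured covariance across strains within subject. Nothing lets that matrix differ by study group.
- **Who is in the fit.** Protocol Table 8 lists all eight strains for about 500 subjects at Visits 1 and 2. SAP 4.3 and Table 4 carry the MenACWY group's Visit 2 titers into the primary analysis as AVISIT 4. SAP 8.1.1 adds: "For each study group, adjusted GMTs, SEs and 80% CI for GMT will be obtained". The restriction to strains common to the groups is attached to the contrasts, not to the data in the model.
- **Secondary analysis.** SAP 8.1.2 leaves MenACWY out.
- **Decision rule.** SAP 8 says ("An acceptable probability of falsely detecting the lymph-node effect was set to 10% (1-sided test"). SAP 8.1.1 says that S "will be declared statistically inferior if the 2-sided 80% CIs of the ratio of the GMT with" D as control is below 1. That rule is not limited to the pooled analysis.

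**The concern.** MenACWY recipients get no B antigen, and rMenBOMV recipients get no A, C, W-135 or Y antigen. With no vaccine response, their later titers can be expected to stay close to baseline, which is already a covariate. SAP 4.3 sets every titer below the LOD to half the LOD, which compresses the spread further. A residual SD smaller than in the vaccinated groups is therefore plausible.

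Under one common variance, that smaller spread lowers the standard error of every contrast between vaccinated groups, although Tables 6 and 7 never use the unexposed group for those strains. The same holds for the adjusted GMRs in SAP 8.2, which use the same model. At stake is whether an interval reported as 80% is an 80% interval when S is declared inferior to D and the plan then reads the lymph-node effect as the most probable cause.

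**Working it through.** **1. The plan's own figure.** Protocol 10.4 assumes 100 per group, a difference of -0.130 log10, and an analysis "with a SD of 0.435 for both groups and a significance level (alpha) of 10% using a 1-sided 2-sample equal-variance t-test". The noncentrality is 0.130 / (0.435 × √(2/100)) = 2.113 on 198 df, which gives power 0.796, as in Table 14. All 16 rows of that table reproduce within 0.0005. This calculation has two vaccinated groups with the same SD and no unexposed group.

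**2. Effect of pooling.** Take k equal groups: k-1 vaccinated with residual SD σ, and one unexposed with SD rσ.

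- Pooled variance = σ² × ((k-1) + r²) / k.
- The SE of a contrast between two vaccinated groups is multiplied by R = √(((k-1) + r²) / k).
- True one-sided error = 1 - Φ(1.2816 × R); coverage = 2Φ(1.2816 × R) - 1.

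In the primary analysis k = 5 for every strain. In the secondary analysis MenACWY is out, so k = 4 for A, C, W-135 and Y, with rMenBOMV unexposed. The secondary B-strain fits have no unexposed group and R = 1.

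Example, primary, r = 0.5: R = √(4.25/5) = 0.922; 1.2816 × 0.922 = 1.182; error 11.9%.

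The range of r is an assumption, because the documents give no SD for an unexposed group.

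| r | R, primary | Error, primary | Coverage, primary | R, secondary A/C/W-135/Y | Error, secondary A/C/W-135/Y |
|---|---|---|---|---|---|
| 0 | 0.894 | 12.6% | 74.8% | 0.866 | 13.4% |
| 0.25 | 0.901 | 12.4% | 75.2% | 0.875 | 13.1% |
| 0.5 | 0.922 | 11.9% | 76.3% | 0.901 | 12.4% |
| 0.75 | 0.955 | 11.0% | 77.9% | 0.944 | 11.3% |
| 1 | 1.000 | 10.0% | 80.0% | 1.000 | 10.0% |
| 1.25 | 1.055 | 8.8% | 82.4% | 1.068 | 8.6% |
| 1.5 | 1.118 | 7.6% | 84.8% | 1.146 | 7.1% |

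On the log scale the CI is thus at most 10.6% too narrow in the primary fits and 13.4% in the secondary A, C, W-135 and Y fits.

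**3. Simulation of the primary layout.** Settings: 5 × 100 subjects, age stratum, 10 centers, baseline covariate, 8,000 runs per scenario (Monte Carlo SE about √(0.10 × 0.90 / 8,000) = 0.34 points). Some scenarios gave the unexposed group a different baseline slope. With all groups in the fit, the error was 11.1% to 12.4% for r from 0.02 to 0.5, and 10.0% at r = 1. With the unexposed group left out it was 9.6% to 10.4%.

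**4. ANCOVA2.** If the unexposed group's covariance matrix is r² times the vaccinated one, a common matrix is scaled by (4 + r²)/5 and the same primary R applies. That proportionality is a further assumption; ANCOVA2 was not simulated.

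**The case against.** The strongest reply has four parts.

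- **Direction is not documented.** No SD, baseline distribution or seronegative share is given for an unexposed group, and the LOD and LLOQ values are left to the study report. With r above 1 the intervals are too wide. A baseline slope that differs in the unexposed group adds residual variance and weakens the effect slightly: at r = 0.5 the mean simulated SE ratio was 0.931, against 0.922 with equal slopes. Unequal variances among the exposed groups, such as one-dose MenACWY against two-dose groups, could also offset it. All of this stands.
- **The 10% rate was designed for another model.** Protocol 10.4 and SAP 4.1 tie it to the S versus D comparison pooled over the B strains, and the text of SAP 8.1.1 assigns the pooled analysis to ANCOVA2. This stands. It moves part of the point to ANCOVA2, which has the same gap. The inferiority rule is not worded as pooled-only, so the strain-level intervals still matter.
- **The study is exploratory.** The plan tests no confirmatory hypothesis, calls its analyses descriptive and makes no multiplicity adjustment. This limits the severity. It does not remove the point, because the plan still states an error rate and a declaration rule.
- **Group-specific variance alone would do, and Protocol 10.8 requires adjusted GMTs for every group.** The second half stands and shapes the fix. On the first half, separate variances do repair the standard errors. But at r = 0.5 each unexposed subject would carry weight 1/0.25 = 4, so 100 of them would count as much as the 400 vaccinated subjects for the common slope, age and center effects. Restricting the contrast fits avoids that.

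A reader might infer that the trial's 10% error rate fails and that the main test is invalid. The documents do not support that: r is unknown, the inflation is bounded, and the secondary B-strain fits are untouched.

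**Conclusion.** The point holds in a limited form. Nothing in SAP 8.1.1, 8.1.2 or 8.2 keeps the antigen-unexposed group out of the ANCOVA1 error variance: MenACWY for B strains in the primary analysis only, and rMenBOMV for A, C, W-135 and Y in both analyses. ANCOVA2 states one covariance matrix for all groups, with MenACWY in its primary fit.

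If r is below 1, the intervals for vaccinated-group contrasts are modestly too narrow. The excess error is 1.0 to 2.6 points in the primary ANCOVA1 for r from 0.75 down to 0, and at most 3.4 points in the secondary A, C, W-135 and Y fits. This rests on equal group sizes, equal variance among the vaccinated groups, and the software default of a single residual variance, since the SAP names the procedure but no variance structure for ANCOVA1. Severity is minor to moderate; it is not a must-fix.

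**What to change.** In SAP 8.1.1, 8.1.2 and 8.2, compute the contrasts from fits restricted to antigen-exposed groups:

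- Primary B strains, and primary ANCOVA2: MenABCWY, S, D, rMenBOMV.
- Primary A, C, W-135, Y: MenABCWY, S, D, MenACWY.
- Secondary A, C, W-135, Y: MenABCWY, S, D only, because MenACWY has no AVISIT 2 record.
- Secondary B strains: groups unchanged.

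State the variance structure explicitly: a residual variance (ANCOVA1) or covariance matrix (ANCOVA2) per study group through REPEATED / GROUP=study group, with Satterthwaite or Kenward-Roger degrees of freedom. Keep the adjusted GMT of the unexposed group, which the protocol requires, as a descriptive output from an all-group fit and label it so.

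The cost is SAP wording, some code, one extra fit per strain and slightly fewer error degrees of freedom. Every contrast in Tables 6 and 7 survives, since none uses an unexposed group for the strain in question. The change of model should be described and justified in the final report, as Protocol 10.11 asks.

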### ANCOVA1

- The fixed-effect model will include age strata, study group, and center as fixed effects. The pre-vaccination (Baseline) log-transformed titer with centering at zero will be included as a continuous covariate.
- The model will be fitted to each serogroup/strain\* separately.

\* a categorical variable will be used to indicate if the dependent variable (response) is for serogroup A, C, W-135, Y or individual serogroup B test strain M14459, 96217, NZ98/254 or M07-0241084.

### ANCOVA2

- The fixed-effect model will include age strata, study group, strain\*\* and center as fixed effects. The pre-vaccination (Baseline) log-transformed titer with centering at zero will be included as a continuous covariate. An interaction between strain\* and pre-vaccination log-transformed titer centered at zero will be included in the model.
- The model will be fitted to the serogroup B test strain data only.

\*\* a categorical variable will be used to indicate if the dependent variable (response) is for serogroup B test strain M14459, 96217, NZ98/254 or M07-0241084.

For each study group, adjusted GMTs, SEs and 80% CI for GMT will be obtained by taking the anti-logarithm of the least squares means, the SE and the lower and upper limits of the 80% CIs of the log-transformed titers. The pre-vaccination log-transformed titer will be zero centered as follows: *log-transformed titer for each subject at Baseline – mean(log-transformed titer for all subjects at Baseline)* i.e. centering will occur after the titer results have been log transformed.

The contrasts in Table 6 will be computed at AVISIT 4 based on PPS3 to investigate possible effects on the immune response based on strains common to each study group.

No adjustment will be made for multiple comparisons.

rMenBOMV+ACWY\_S will be declared statistically inferior if the 2-sided 80% CIs of the ratio of the GMT with rMenBOMV+ACWY\_D as control is lower than 1 at 1 month after last vaccination. The lymph-node effect would therefore be the most probable cause for the decrease observed.

**Table 6 Contrasts for GMT from ANCOVA Models - Primary**

Contrast	Serogroup and Strains	Model
rMenBOMV+ACWY_S versus rMenBOMV+ACWY_D (test for immune interference, due to immunological stress to lymph node)	A, C, W-135, Y Individual B strains Pooled B strains	ANCOVA1
MenABCWY versus rMenBOMV+ACWY_S (test for other unknown immunological interference)		ANCOVA1
rMenBOMV+ACWY_S versus rMenBOMV		ANCOVA1
rMenBOMV+ACWY_S versus MenACWY	A, C, W-135, Y	ANCOVA1
rMenBOMV+ACWY_D versus rMenBOMV	Individual B strains	ANCOVA1
rMenBOMV+ACWY_D versus MenACWY	A, C, W-135, Y	ANCOVA1
MenABCWY versus rMenBOMV	Individual B strains	ANCOVA1
MenABCWY versus MenACWY	A, C, W-135, Y	ANCOVA1

The following outputs will be produced:

- Unadjusted and adjusted summary statistics (n, GMT, GSD, 80% CI for GMT, minimum, maximum, ANCOVA results: GMT, SE, 80% CI for GMT) at Baseline and AVISIT 4, based on PPS3.
- Contrasts from Table 6.

### 8.1.2 Secondary Endpoint

The analyses described in Section 8.1.1 will be repeated using AVISIT 2 instead of AVISIT 4, with the exception that the contrasts defined in Table 7 will be calculated (instead of Table 6). The MenACWY study group is not included in the secondary analyses.

**Table 7 Contrasts for GMT from ANCOVA Models - Secondary**

Contrast	Serogroup and Strains	Model
rMenBOMV+ACWY_S versus rMenBOMV+ACWY_D (test for immune interference, due to immunological stress to lymph node)	A, C, W-135, Y	ANCOVA1
	Individual B strains	ANCOVA1
	Pooled B strains	ANCOVA2
MenABCWY versus rMenBOMV+ACWY_S (test for other unknown immunological interference)	A, C, W-135, Y Individual B strains	ANCOVA1 ANCOVA1
rMenBOMV+ACWY_S versus rMenBOMV	Individual B strains	ANCOVA1
rMenBOMV+ACWY_D versus rMenBOMV	Individual B strains	ANCOVA1
MenABCWY versus rMenBOMV	Individual B strains	ANCOVA1

The following outputs will be produced:

- Unadjusted and adjusted summary statistics (n, GMT, GSD, 80% CI for GMT, minimum, maximum, ANCOVA results: GMT, SE, 80% CI for GMT) at Baseline and AVISIT 2 based on PPS4.
- Contrasts from Table 7.

## 8.2 Geometric Mean Ratios

### 8.2.1 Primary Endpoint

GMR will be summarized by study group at AVISIT 4 for each serogroup (A, C, W-135, Y) and the four individual serogroup B test strains. Missing titer results and results below the LOD will be handled as described in Section 4.3.

Unadjusted and adjusted summaries will be calculated and presented in the same output.

GMR will be calculated as the anti-logarithm of the mean of the change from baseline of log-transformed titer values at AVISIT 4 and Baseline i.e. anti-logarithm of  $\sum(\log_{10}(\text{titer}_{\text{AVISIT 4}}) - \log_{10}(\text{titer}_{\text{Baseline}}))/n$  where n is the number of subjects with non-missing titer results at Baseline and AVISIT 4.

Unadjusted summaries will include the number of subjects with non-missing titer results at AVISIT 4, GMR, GSD of the difference in log-transformed titer results at AVISIT 4 and Baseline, 80% CI for GMR, minimum and maximum.

GSD will be calculated as the anti-logarithm of the SD of the change from baseline of the log-transformed data. The 80% CI for GMR will be calculated as the anti-logarithm of the endpoints of the 80%CI for the mean GMR. The anti-logarithm is calculated as  $10^x$  where  $x$  is the statistic of interest calculated from the log-transformed data (e.g. mean, SD, 80% CI endpoints).

Adjusted summaries will be calculated using an ANCOVA model. The adjusted GMR, SE and 80% CI from the ANCOVA model will be presented. ANCOVA1 from Section 8.1.1 will be fitted to each serogroup/strain individually.

For each study group, adjusted GMRs, SEs and 80% CI for GMR will be obtained by taking the anti-logarithm of the least squares means, the SE and the lower and upper limits of the 80% CIs of the difference between log-transformed titers. The pre-vaccination log-transformed titer will be zero centered as follows: *log-transformed titer for each subject at Baseline – mean(log-transformed titer for all subjects at Baseline)* i.e. centering will occur after the titer results have been log transformed.

The contrasts in Table 6 will be computed (ANCOVA1 only) based on PPS3 to investigate possible effects on the immune response based on strains common to each study group.

No adjustment will be made for multiple comparisons.

The following results will be produced and presented in the same output containing the results from Section 8.1.1:

- Unadjusted and adjusted summary statistics (n, GMR, GSD, 80% CI for GMR, minimum, maximum, ANCOVA results: GMR, SE, 80% CI for GMT), based on PPS3.
- Contrasts from Table 6 (ANCOVA1 only).

### **8.2.2 Secondary Endpoint**

The analyses described in Section 8.2.1 will be repeated using AVISIT 2 instead of AVISIT 4, with the exception that the contrasts defined in Table 7 will be calculated. The MenACWY study group is not included in the secondary analyses.

The following results will be produced and presented in the same output containing the results from Section 8.1.2:

- Unadjusted and adjusted summary statistics (n, GMR, GSD, 80% CI for GMR, minimum, maximum, ANCOVA results: GMR, SE, 80% CI for GMT), based on PPS4.
- Contrasts from Table 7 (ANCOVA1 only).

